5.1.1 Safety Review Committee

An internal Safety Review Committee will assess BP data after completion of the Sentinel Group. The Committee may request access to unblinded treatment codes for individual participants. The Committee will consist of senior clinical development individuals not directly involved in the study conduct and overseeing, including (but not limited to) senior Worldwide Patient Safety representative, a statistician, and a senior clinician.

5.2 Number of Participants

It is estimated that a total of approximately 72 participants will be randomized with 1:1 ratio assigned to either BMS-986259 subcutaneous QD or Placebo to have at least 60 completers by the end of the study.

5.3 End of Study Definition

The study treatment's duration is 14 days with an on-site follow-up visit on Day 30 (\pm 2 days).

[figure not shown]
[REDACTED] The start of the trial is defined as the first visit of the first participant screened. End of trial is defined as last treatment visit and last follow-up visit of the last participant to complete the study. Study completion is defined as the final date on which data for the primary endpoint was or is expected to be collected, if this is not the same.

5.4 Scientific Rationale for Study Design

Relaxin exhibits vasodilatory effect and BMS-986259 is expected to demonstrate similar properties including potential for lowering blood pressure. Serelaxin's development program provided extensive data in patients treated for ADHF. Small difference from placebo was observed in the absolute SBP lowering, however a substantially larger proportion of patients demonstrated clinical AEs related to BP reduction. In the RELAX-AHF study, confirmed events of decreased blood pressure were reported in 18% and 29% in the placebo vs the active group, respectively.²⁶ In contrast, in the RELAX-REPEAT study conducted in chronic stable HF patients, there was no observed difference in blood pressure between serelaxin and placebo.¹⁹ No data are available on the risk of clinically significant hypotension with relaxin administered to medically stabilized patients admitted for ADHF, especially in the group with SBP < 125 mmHg which was an exclusion criterion in the serelaxin program. Hypotension is one of the factors prohibiting treatment optimization with standard of care HF medications; thus, a new treatment that would be safe and well tolerated in patients with lower range of BP would be clinically valuable. This study will allow to establish safety and tolerability of BMS-986259 with regards to the risk of hypotension in such population. The population of HF patients early after admission for ADHF has the highest rates of mortality and rehospitalization, with the rates as high as 14% and 30% within 60 to 90 days, respectively.³⁰ This represents a high unmet need for both patients with HFrEF and HFpEF.

The duration of the study is limited by the availability of the current toxicology data (up to 2 weeks). The primary goal of the study is safety and tolerability. Fourteen days should be sufficient to establish potential for hypotension to inform further development BP margins and help to inform the design of Phase 2 / Phase 3 studies. Based on the data from the ongoing Phase 1 trial, steady state is achieved after approximately 5 days. Study duration will allow to observe participants after they achieved steady state and a minimum hospital stay of 5 days after randomization will ensure more intense monitoring while the exposures of the study drug are still increasing.

The secondary [REDACTED] efficacy endpoints include PK [REDACTED] [REDACTED] which will provide an initial supportive data for the mechanism of action in heart failure population.

Finally, serum PK will be measured to validate data collected from Phase 1 in normal healthy volunteers and further inform dosing in Phase 2.

5.5 Justification for Dose

The planned dose for this study (3 mg) has been selected as a pharmacologically active and safe dose, likely to be further studied in Phase 2B, thus safety/tolerability data collected in this study will inform design of the Phase 2B study. The BMS-986259 dose selected for this study (3 mg) was associated with improvement in RBF after single and multiple doses in normal healthy participants (up to 46% increase in RBF). The 3 mg multiple doses in FIH study were also safe and well tolerated by the healthy participants.

In the FIH study (CV019002), single doses as much as 5-fold higher (15 mg) have been safely administered to healthy participants. The observed mean exposures at steady state with repeated 3 mg QD dosing (AUC[TAU]) of 9,070 ng h/mL remain under the mean exposure (AUC[INF]) of 38,200 ng h/mL observed after a single 15 mg dose that was determined to be safe and well tolerated in a healthy participants study (Table 5.5-1).

Based on preliminary results, single dose exposures (C_{max} and area under the concentration-time curve [AUC]) increased in a dose-proportional manner with increasing dose. With multiple doses of 1 mg and 3 mg QD for 14 days, up to 2.5-fold (1 mg) and 2.7-fold (3 mg) accumulation of C_{max} and AUC(TAU) were observed on Day 14 versus Day 1, with steady-state reached within approximately 5 days based on trough concentrations. The geometric mean C_{max} and AUC values observed with a single 15 mg dose and a 3 mg QD dose are listed in Table 5.5-1.

Table 5.5-1: BMS-986259 Exposures in Healthy Participants

Dose	C _{max} (ng/mL) Geometric Mean	AUC (ng·h/mL) Geometric Mean
15 mg single dose	737	38,200*
3 mg QD, Day 1	184	3,420
3 mg QD, Day 14	469	9,070

* AUC(INF)

Abbreviations: AUC = area under the curve; C_{max} = maximum observed concentration; QD = once daily.

A short-acting recombinant form of human H2-relaxin, serelaxin, dosed IV, demonstrated vasodilatory properties and enhanced both RBF and eGFR in patients with HF.^{18,19,20} In previous studies, serelaxin was safely administered IV for up to 48 hours in healthy participants and over 4,000 patients with HF and produced increases in RBF and GFR, as well as improvements in multiple hemodynamic parameters and biomarkers of cardiac and renal function.^{18,19,20,23,24,25,26} Based on the potency ratio between serelaxin and BMS-986259, it is anticipated that the 3 mg dose of BMS-986259 is consistent with the doses found to be efficacious, safe and well tolerated in heart failure patients in the serelaxin development program.

6 STUDY POPULATION

For entry into the study, the following criteria **MUST** be met.

6.1 Inclusion Criteria

1) Signed Written Informed Consent

- a) Participants must be willing to participate in the study and provide a written ICF.
- b) Participants must be willing and able to communicate and complete all study-specific procedures and visits.

2) Type of Participant and Target Disease Characteristics

- a) Patients currently hospitalized for ADHF, regardless of Left Ventricular Ejection Fraction (LVEF) ≥ 24 hours since presentation to ER defined as the time of the first dose of IV diuretic administered at the hospital, maximum of 8 days since presentation to ER and before hospital discharge.
 - i) ADHF is the main reason for admission and there is no other potential cause for congestive symptoms leading to index hospitalization (eg, concurrent pneumonia, acute chronic obstructive pulmonary disease [COPD] exacerbation).
 - ii) Dyspnea at rest or with minimal exertion upon presentation to ER, plus signs and symptoms of fluid overload that require IV therapy with loop diuretics.
 - iii) NT-proBNP ≥ 1400 pg/mL OR BNP ≥ 350 pg/mL upon presentation to the hospital; NT-proBNP ≥ 2000 pg/mL OR BNP ≥ 500 pg/mL if Atrial Fibrillation (AFib) present at presentation. For participants on Entresto, NT-proBNP should be used.
- b) Patients must be hemodynamically stable, as assessed by the investigator, and as defined by the following criteria:
 - i) ≥ 12 hours since the last dose change of IV loop diuretics (ie, participants may still be on IV loop diuretics at randomization, as long as dose is stable ≥ 12 hours).
 - ii) ≥ 24 hours since last dose of positive inotropes.
 - iii) ≥ 12 hours since the last dose of IV vasodilators.
 - iv) Absence of symptoms of hypotension (eg, dizziness, lightheadedness, etc).
 - v) Supine SBP (supine position is preferable, based on participant's condition and comfort) must remain within the following range, on at least 2 routine consecutive measurements, over the 12 hours before randomization:
 - (1) Sentinel Group: SBP ≥ 115 mmHg.
 - (2) Main Group: SBP ≥ 100 mmHg.

3) Age and Reproductive Status

Investigators shall counsel male participants who are sexually active with women of childbearing potential (WOCBP), on the importance of pregnancy prevention, the implications of an unexpected pregnancy and the potential of fetal toxicity occurring due to transmission of study drug, present in seminal fluid, to a developing fetus, even if the participant has undergone a successful vasectomy or if the partner is pregnant.

- Local laws and regulations may require the use of alternative and/or additional contraception methods.
 - a) Female Participants
 - i) Females, ages at least 18 or local age of majority (See [Appendix 7](#) for maximum age limit where locally mandated).
 - ii) A female participant is eligible to participate if she is not pregnant or breastfeeding, and is not a WOCBP.
 - iii) Women participants must have documented proof that they are not of childbearing potential.
 - iv) Women must not be breastfeeding.
 - b) Male Participants
 - i) Males, ages at least 18 or local age of majority (See [Appendix 7](#) for maximum age limit where locally mandated).
 - ii) Males who are sexually active with WOCBP must agree to follow instructions for method(s) of contraception defined in [Appendix 4](#) and as described below.
 - (1) For males who are sexually active with WOCBP, less than highly effective methods of contraception and unacceptable methods of contraception are not permitted.
 - (2) Hormonal contraception is also not permitted.
 - iii) Azoospermic males are not exempt from contraceptive requirements and will be required to always use a latex or other synthetic condom during any sexual activity (eg, vaginal, anal, oral) with WOCBP even if the participant has undergone a successful vasectomy or if the partner is pregnant or breastfeeding.
 - iv) Male participants will be required to always use a latex or other synthetic condom during any sexual activity (eg, vaginal, anal, oral) with WOCBP; even if the participants have undergone a successful vasectomy or if their partner is already pregnant or breastfeeding. Males should continue to use a condom during the intervention period and for at least 6 days after the last dose of study intervention.
 - v) Female partners of males participating in the study should be advised to use highly effective methods of contraception during the intervention period and for at least 6 days after the last dose of study intervention in the male participant.
 - (1) For female partners of males participating in the study, less than highly effective methods of contraception and unacceptable methods of contraception are not permitted.
 - (2) Hormonal contraception is also not permitted.

- vi) Male participants with a pregnant or breastfeeding partner must agree to remain abstinent from sexual activity or use a male condom during any sexual activity (eg, vaginal, anal, oral) even if the participants have undergone a successful vasectomy, during the intervention period and for at least 6 days after the last dose of study intervention.
- vii) Male participants must refrain from donating sperm during the intervention period and for at least 6 days after the last dose of study intervention.
- viii) Breastfeeding partners should be advised to consult their health care providers about using appropriate highly effective contraception during the time the participant is required to use condoms.

6.2 Exclusion Criteria

1) Target disease exceptions

- a) At randomization systolic blood pressure < 100 mmHg or > 145 mmHg.
- b) At randomization HR > 120 bpm.
- c) Acute cardiovascular condition other than HF decompensation either contributing to hospitalization or making participant unstable, such as acute MI/acute coronary syndrome, myocarditis, or arrhythmia with the exception of atrial fibrillation if HR within criteria limit.
- d) Cardiogenic shock (defined as SBP below 90 mmHg, signs of end-organ hypoperfusion plus need for intubation, mechanical circulatory support and other life-sustaining emergency measures) at presentation to ER or at any time before randomization.
- e) History of heart or any other solid organ transplant or currently on the transplant list.
- f) Recipient of ventricular assist devices.
- g) Use of any cardiac extracorporeal devices, within 12 weeks of study randomization. Cardiac Resynchronization Therapy Defibrillator (CRTD) and pacemakers/Implantable Cardioverter-Defibrillator (ICDs) are allowed, if implanted at least 4 weeks before randomization and no discharge within 4 weeks prior to randomization.
- h) Participants with contraindications to vasodilator therapy such as restrictive or obstructive cardiomyopathy, severe mitral or aortic stenosis.

2) Medical History and Concurrent Diseases

- a) Women cannot be pregnant or breastfeeding.
- b) Any major surgery within 12 weeks of study randomization.
- c) Suspected acute pulmonary disease such as pneumonia, exacerbation of asthma or COPD or severe chronic, pulmonary disease (eg, severe COPD, pulmonary fibrosis, patients with hypercapnia or requiring home oxygen or chronic systemic steroids)
- d) Hereditary or idiopathic pulmonary hypertension.
- e) History of stroke, or transient ischemic attack (TIA) within the 30 days prior to screening (according to the participants' records) or during screening.
- f) Acute coronary event within 30 days prior to screening or during screening (myocardial infarction, acute coronary syndrome, or unstable angina; according to the participants' records).

- g) Terminal non-cardiovascular disease such as cancer with life expectancy < 6 months.
- h) Severe liver disease such as cirrhosis with evidence of portal hypertension, or acute viral hepatitis.
- i) Participant is on dialysis or history of chronic or intermittent dialysis or ultrafiltration.
- j) Need for mechanical ventilation any time before screening or non-invasive ventilation (CPAP, BiPAP) < 2 hrs prior to screening.

3) Prior/Concomitant Therapy:

- a) Inability to comply with restrictions and prohibited treatments as listed in [Section 7.7](#) Concomitant Therapy. The following are prohibited before and during the study:
 - a. Phosphodiesterase type 5 (PDE5) inhibitors used for erectile dysfunction: sildenafil, tadalafil, vardenafil, etc (within 48 hours of initial study drug administration and throughout the study, up to 5 days after the last dose of study drug).
 - b. Continuous infusion of IV diuretics, inotropes and vasodilators during the study.
- b) Guidelines Directed Medical Therapy (GDMT) for HF is allowed, either at screening or during the study, as clinically warranted.
- c) Exposure to any investigational drug or placebo, including serelaxin; within 30 days of initial study drug administration or 4 months prior to the first dose of IP, in case of exposure to long-acting biological investigational drug.

4) Laboratory Test Findings

- a) Participant has key laboratory testing findings within the following ranges:
 - i) Persistent electrolytes abnormalities not corrected before randomization
 - (1) A sodium concentration < 130 or > 145 mEq/l.
 - (2) A potassium concentration < 3.1 or > 5.5 mEq/l.
 - ii) Hemoglobin < 9 g/dL, which is defined as severe anemia.
 - iii) eGFR < 30 ml/min./1.73 m².
 - iv) **Not applicable per Revised Protocol 01**
 - v) Positive blood screen for hepatitis C antibody, hepatitis B surface antigen, or human immunodeficiency virus (HIV)-1 and -2 antibodies.
 - vi) Liver abnormalities including total bilirubin > 1.5 × upper limit of normal (ULN) or significant elevation of liver enzymes (aspartate aminotransferase [AST] or alanine aminotransferase [ALT] > 3 × ULN).
 - vii) Positive RT-PCR test or rapid antigen test for SARS-CoV-2 prior to randomization.

5) Allergies and Adverse Drug Reaction

- a) History of any significant drug allergy or drug-related SAE (such as anaphylaxis or hepatotoxicity).
- b) History of ADAs to relaxin (eg, while in a serelaxin development program).
- c) History of adverse reactions to aminoglycosides.

6) Other Exclusion Criteria

- a) Prisoners or participants who are involuntarily incarcerated. (Note: under certain specific circumstances and only in countries where local regulations permit, a person who has been

imprisoned may be included or permitted to continue as a participant. Strict conditions apply and BMS approval is required.)

- b) Employees of CRO or BMS and their first-line relatives.
- c) Legal incapacity or limited legal capacity.

Eligibility criteria for this study have been carefully considered to ensure the safety of the study participants and that the results of the study can be used. It is imperative that participants fully meet all eligibility criteria. No waivers will be provided.

6.3 Lifestyle Restrictions

Not applicable. No restrictions are required.

6.4 Screen Failures

Screen failures are defined as participants who consent to participate in the clinical study but who are not subsequently **randomized** in the study/included in the analysis population. A minimal set of screen failure information is required to ensure transparent reporting of screen failure participants, to meet the Consolidated Standards of Reporting Trials (CONSORT) publishing requirements, as applicable, and to respond to queries from regulatory authorities. Minimal information includes date of consent, demography, screen failure details, eligibility criteria, and any serious AEs.

6.4.1 Retesting During Screening or Lead-In Period

In an effort to find all possible well-qualified participants, participants who have discontinued the study as a screen failure (have not been randomized) are eligible for re-screening upon presentation for a subsequent episode of ADHF, at the discretion of the investigator. If re-screened, the participant must be re-consented and a new participant number will be assigned by the IRT. Laboratory parameters and/or assessments that are included in [Table 2-1](#) (Screening Procedural Outline) and [Table 2-2](#) (On-treatment and Follow-up Procedural Outline), must be repeated. The participant numbers and data will be linked in the clinical database.

All screening laboratory testing will be performed locally, and tests may be repeated at the discretion of the Investigator as per site policy.

Any new result will override the previous result. The most current result prior to Randomization is the value by which study inclusion will be assessed, as it represents the participant's most current, clinical state.

7 TREATMENT

Study treatment is defined as any investigational treatment(s), marketed product(s), placebo or medical device intended to be administered to a study participant according to the study randomization or treatment allocation.

Study treatment includes both IP and Non-investigational Product (Non-IP) as shown in [Table 7-1](#).

An IP, also known as investigational medicinal product (IMP) in some regions, is defined a pharmaceutical form of an active substance or placebo being tested or used as a reference in a clinical study, including products already with a marketing authorization but used or assembled (formulated or packaged) differently than the authorized form, or used for an unauthorized indication, or when used to gain further information about the authorized form.

Other medications used as support or escape medication for preventative, diagnostic, or therapeutic reasons, as components of the standard of care for a given diagnosis, may be considered as non-IPs.

Table 7-1: Study treatments for CV019010					
Product Description / Class and Dosage Form	Potency	IP/ Non-IP	Blinded or Open Label	Packaging / Appearance	Storage Conditions (per label)
BMS-986259 injection for SC administration	5 mg/vial (5 mg/mL) Dose level 3 mg and 1 mg BMS-986259 will be diluted to administer a 3 mg or 1 mg dose as a 1 mL SC injection. Details of preparation and administration are provided in the pharmacy manual	IP	Blinded	Colorless to pale yellow liquid in vial	Refer to the label on the container and/or the pharmacy manual
Placebo injection for SC administration	N/A	IP	Blinded	Colorless to pale yellow liquid in vial	Refer to the label on the container and/or the pharmacy manual
Placebo injection to be utilized as diluent	N/A	IP	Open Label	Colorless to pale yellow liquid in vial	Refer to the label on the container and/or the pharmacy manual

Abbreviations: IP = Investigational Product; N/A = not applicable; Non-IP = Non-investigational Product; SC = subcutaneous.

BMS-986259 is not intended for participant's self-administration.

7.1 Treatments Administered

The selection and timing of dose for each participant is as follows:

Table 7.1-1: Selection and Timing of Dose

Study Treatment	Unit dose strength(s)/Dosage level(s)	Dosage formulation Frequency of Administration	Route of Administration
BMS-986259	3 mg ^a , 1 mg ^{a,b}	Daily	Subcutaneous injection
Placebo	N/A	Daily	Subcutaneous injection

^a 5 mg/mL solution will be diluted as described in the pharmacy manual to reach the desired dosage strength

^b 1 mg for down titration only

In the morning on Days 1 through 14 each participant will receive a subcutaneous dose of BMS-986259 or placebo, at approximately the same time.

The time of dose administration of the first dose will be called “0” hour for serum PK reporting.

7.2 Method of Treatment Assignment

All participants will be centrally randomized using an Interactive Response Technology (IRT). Before the study is initiated, each user will receive log in information and directions on how to access the IRT.

Study treatment will be dispensed at the Day 1 visit.

At the time of screening for both the Sentinel Group and Main Group, participants will be randomized to receive either BMS-986259 or placebo in a 1:1 ratio according to a computer-generated randomization scheme prepared by a Randomization Coordinator within the Drug Supply Management Department of BMS Research and Development.

Enrolled participants, including those not dosed, will be assigned sequential participant numbers starting with 00001, (eg, 00001, 00002, 00003.... 00010). Sequential numbering may restart at 00001 for each participating site as the distinct patient identification number (PID) will ultimately be comprised of the site number and participant number, (eg, 0002 00001). Those enrolled participants meeting inclusion and exclusion criteria will be eligible to be randomized. Randomization numbers will be assigned prior to dosing.

During the screening visit, the investigative site will call into the enrollment option of the Interactive Response Technology (IRT) designated by BMS for assignment of a 5-digit participant number that will be unique across all sites. For example, the first participant screened (ie, enrolled) at site number 1, will have a PID of 0001 00001. Once it is determined that the participant meets the eligibility criteria following the screening visit, the investigative site will call the IRT to randomize the participant.

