3.1 Study Rationale

The main purpose of this trial is to evaluate the effect of BMS-986259 on blood pressure (BP) events defined as symptomatic hypotension or hypotension requiring study drug discontinuation, in hospitalized HF patients stabilized after an admission for ADHF. The study is designed to provide data on the range of BP in which BMS-986259 is safe and well tolerated in the context of the current hospitalization for ADHF. It also aims to provide additional rationale for future development, future clinical use and to inform the design of the next Phase 2-3 studies. In addition, this study will provide initial data on the pharmacokinetics of BMS-986259 in HF participants.

Standard of care in the treatment of ADHF involves the use of IV loop diuretics and vasodilators, which may predispose participants to hypotension, with or without symptoms. Current guidance

also recommends continuing Guidelines Directed Medical Therapy (GDMT) including angiotensin-converting enzymes (ACE), beta-blockers, MRAs/mineralocorticoid receptor inhibitors (MRI), and angiotensin receptor-neprilysin inhibitors (ARNI), which may also lower BP. In the Serelaxin ADHF study, RELAX-AHF, greater reductions from baseline in SBP were observed during IV infusion up to 48 hours in the serelaxin group ($-16.5 \text{ mmHg} \pm 17.2$) compared with placebo ($-12.3 \text{ mmHg} \pm 17.2$). Also, more participants on serelaxin than on placebo had protocol required blood pressure-related dose reduction (29% vs 18%) or drug discontinuation (19% vs 12%).²⁶ In contrast, in the chronic stable HF population of the RELAX REPEAT study, SBP in the serelaxin group did not differ from placebo.¹⁹ There are no data on the effect of relaxin on BP in the population of HF patients admitted for ADHF, but not yet discharged, already medically stabilized and weaned from IV vasodilators or inotropes.

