Participants will return for up to three ambulatory visits at the site on Day 8, Day 14, Day 30 (follow-up). If the participant cannot return to the site because of COVID-19 local regulations that prevent visits in-person, these visits can be done at home by the home nurse in discussion with the Principal Investigator (or designee). In addition, at discharge, participants will receive BP measuring device and will be instructed to measure BP if symptoms consistent with hypotension occur. If systolic BP falls below 85 mmHg (on 2 repeated measurements within 30 minutes) and symptoms of hypotension persist, participants will be instructed to report to the study site or another healthcare provider if the study site cannot be reached.

Initially participants with SBP ≥ 115 mmHg will qualify to be randomized 1:1 to receive 3 mg subcutaneous BMS-986259 QD or placebo. After approximately 8 participants with SBP ≥ 115 and < 130 mmHg have completed the treatment period, the Safety Review Committee will review the safety data from this sentinel group and ensure it is safe to proceed with the Main Group, ie., open the recruitment for participants with SBP less than 115 mmHg (but at least 100 mmHg).

The Main Group will include participants with SBP ≥ 100 mmHg, randomized 1:1 to BMS-986259 or placebo. The proportion of participants with SBP > 125 mmHg will be capped at 48 participants.

Study drug may be down-titrated to 1 mg or discontinued according to the criteria described in dose modification in [Section 7.4](#).

In addition, if systolic BP is < 85 mmHg or symptomatic hypotension occurs, the Principal Investigator (or designee; must be a medical doctor [MD]) must be contacted to make a decision

[figure not shown]

as to whether an ambulatory unscheduled study visit or hospitalization is required based on overall clinical assessment. For example, asymptomatic study participants who can walk and have normal urination may not require hospitalization. BMS Study Director/Medical Monitor (or designee) must be notified. A blinded clinical contact will be available 24/7 to answer questions and guide the home nurse as needed.

The study design schematic is presented in [Figure 5.1-1](#).

Figure 5.1-1: Study Design Schematic

Abbreviations: [REDACTED] D = day; ER = emergency room; [REDACTED] QD = once daily; R = randomization; SBP = systolic blood pressure.

^a May be down-titrated to 1 mg or discontinued according to the criteria described in Section 7.4.

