10 STATISTICAL CONSIDERATIONS

10.1 Sample Size Determination

The primary objective of the study is to evaluate safety and tolerability of BMS-986259. It is estimated there may be ~10% to 20% early treatment withdrawal. Approximately 72 participants will be randomized with 1:1 ratio to BMS-986259 subcutaneous QD and Placebo to have at least 60 completers by the end of the study. An estimation approach will be used for comparison between BMS-986259 and placebo for hypotension rate. Point estimates and associated 95% confidence intervals for event rate and relative risk ratio will be constructed to provide plausible range of values for the true comparison of interest.

The incidence of clinically relevant hypotension in the placebo group is estimated to be between ~ 5% to 15%. With N=60 and 1:1 treatment assignment ratio, the study will be able to detect a significant increase of clinical hypotension event compared to placebo ranging from 2.7 fold increase (eg, placebo rate =15%) to 5 fold increase (eg, placebo rate =5%).

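### Section 7.2 names no stratification factor and Section 10.3.2 no SBP adjustment, although baseline SBP shapes both the primary endpoint and the design

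*Combined protocol and SAP*

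**What the plan says.** Section 7.2 (Method of Treatment Assignment) covers the Sentinel and Main Groups together: "participants will be randomized to receive either BMS-986259 or placebo in a 1:1 ratio according to a computer-generated randomization scheme". Randomisation is central, through the IRT. No stratification factor, block size or minimisation is given. Section 5.1 repeats the ratio: "The Main Group will include participants with SBP ≥ 100 mmHg, randomized 1:1 to BMS-986259 or placebo". Section 10.1 gives the size: "Approximately 72 participants will be randomized with 1:1 ratio to BMS-986259 subcutaneous QD and Placebo to have at least 60 completers".

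For the analysis, Section 10.3.2 plans event rates by treatment, with the risk difference, relative risk and 95% confidence intervals. It mentions no stratification or covariate.

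Baseline SBP appears throughout the design:

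- **Endpoint (Section 4):** confirmed supine SBP below 85 mmHg, or below 90 mmHg with symptoms.
- **Entry range (Sections 6.1 and 6.2):** 100 to 145 mmHg.
- **Gate and cap (Section 5.1):** 115 mmHg or more at first, with lower values admitted after safety review; at most 48 participants above 125 mmHg.
- **Interim (Section 10.3.5):** about 30 completers, about 15 of them at or below 125 mmHg.
- **Aim (Section 3.1):** "The study is designed to provide data on the range of BP in which BMS-986259 is safe and well tolerated".

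**The concern.** Because the endpoint is a fixed pressure, distance to it depends on where a participant starts. Someone entering at 102 mmHg falls below 85 after a drop of more than 17 mmHg; someone entering at 140 needs more than 55. Baseline SBP should therefore be a strong predictor of the event, and the plan's gate, cap and interim condition treat it as important.

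As written, neither the allocation nor the analysis protects the comparison from an uneven split of low-pressure participants. With about 36 per arm and few events, such a split can look like a drug effect or hide one. It also unbalances the within-band comparison that the stated aim calls for, both at the interim and at the end.

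**Working it through.** **1. The plan's own figure.** Section 10.1 states a detectable 2.7-fold increase at a 15% placebo rate and 5-fold at 5%, with N = 60 (30 per arm). It gives no power or sidedness. For a two-sided 5% test,

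power = Φ{[(p2 − p1) − 1.96·√(2p̄(1 − p̄)/30)] / √([p1(1 − p1) + p2(1 − p2)]/30)}.

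- 15% v 40.5%: (0.255 − 0.2266)/0.1108 = 0.256, so power is 60.1%.
- 5% v 25%: (0.200 − 0.1807)/0.0885 = 0.218, so power is 58.6%.

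The stated folds correspond to about 60% two-sided power. They do not depend on the point made here, but they show how little precision there is to spare.

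**2. Size of the low band.** Reading the cap as applying to the whole trial, 72 − 48 = 24 is the smallest number at or below 125 mmHg if 72 are randomised.

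**3. Chance of an uneven split.** Let X be the number of the 24 who are in the active arm. With arms fixed at 36:36, X is hypergeometric (72, 24, 36). With simple randomisation, X is approximated as binomial (24, 0.5). Both directions are counted.

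| Split or worse | Arms 36:36 | Simple randomisation |
|---|---|---|
| 14:10 | 45.4% | 54.1% |
| 15:9 | 21.1% | 30.7% |
| 16:8 | 7.9% | 15.2% |

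A surplus of 15 or more in the active arm alone has a 10.5% chance with 36:36 arms. The chance of an arm difference of 6 or more is 11.1% with 12 low-band participants and 23.8% with 36. At the interim (15 low-band of 30), a 10:5 split or worse has a 14% chance with 15:15 arms and 30% with simple randomisation.

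**4. Effect of a 15:9 split with an inert drug.** The documents give no event rate by SBP band, so the rates below are assumptions.

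Active rate = (15·pL + 21·pH)/36; placebo rate = (9·pL + 27·pH)/36; risk difference = (pL − pH)·6/36.

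| pL (≤125) | pH (>125) | Overall | Active | Placebo | Risk difference | Relative risk |
|---|---|---|---|---|---|---|
| 20% | 5% | 10.0% | 11.25% | 8.75% | 2.5 points | 1.29 |
| 25% | 5% | 11.7% | 13.3% | 10.0% | 3.3 points | 1.33 |
| 30% | 5% | 13.3% | 15.4% | 11.25% | 4.2 points | 1.37 |
| 11% | 2% | 5.0% | 5.75% | 4.25% | 1.5 points | 1.35 |

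All four overall rates lie within the plan's 5-15% for placebo. In the last row the risk difference shrinks but the relative risk does not.

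**5. Long-run behaviour.** This was simulated with 40,000 runs, 36 per arm and 24 low-band participants. The drug effect, where present, is 2.7-fold. The adjusted analysis is Mantel-Haenszel/CMH by SBP band.

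| Quantity | 20% / 5%: unstratified allocation | 20% / 5%: stratified | 30% / 5%: unstratified | 30% / 5%: stratified |
|---|---|---|---|---|
| SD of crude risk difference, no effect (points) | 7.1 | 6.9 | 8.1 | 7.5 |
| SD of crude risk difference, 2.7-fold (points) | 8.8 | 8.3 | 9.5 | 8.0 |
| Power, crude test | 46% | 46% | 62% | 63% |
| Power, SBP-stratified test | 51% | 52% | 76% | 77% |

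With no effect, the mean risk difference is zero to within simulation error. The crude test's one-sided false-positive rate under unstratified allocation is 2.7-3.0%, against a nominal 2.5%.

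**The case against.** The strongest reply is that stratification in a 72-participant Phase 2A estimation study is a preference, and that little is lost without it. Much of this stands. Averaged over randomisations there is no bias, the false-positive rate stays near nominal, and the planned confidence intervals already largely carry this chance variation. A relative risk of 1.29-1.37 is small beside the 2.7- to 5-fold increases in Section 10.1. The interim is for planning, with no stopping rule stated in Section 10.3.5. Baseline characteristics will be tabulated, so an imbalance would be seen. Most of the recoverable power comes from a stratified analysis, not from stratified allocation.

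Two stronger readings are tempting, and the documents do not support them:

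- A reader might infer that allocation is definitely unstratified. Section 7.2 is silent; it does not say so, and its wording does not rule out separate schedules for the two groups.
- A reader might infer that the IRT already holds SBP because it must run the gate and the cap. No section says who enforces either. Only the site is shown to know SBP before randomisation.

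The reply does not remove the point. This trial will be run once, and seeing an imbalance in a baseline table does not correct the estimate. With no adjusted estimate pre-specified, any correction would be chosen after the data are known. Stratified allocation is also the only step that secures similar low-band numbers in each arm, which the tolerated-range aim needs.

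**Conclusion.** The point holds as an improvement worth making. It is not an error in a stated figure, nor a contradiction between sections. No stratification factor and no SBP adjustment are stated, and a 15:9 split or worse in the low band has about a one-in-five chance with equal arms (21%; 31% with simple randomisation). Under an inert drug and the assumed rates, that split moves the expected relative risk to 1.29-1.37 and the risk difference by 2.5-4.2 points, or by 1.5 points at rates of 11% and 2%.

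A reader might conclude that the primary comparison is biased. It is not: the cost is balance, precision and interpretability in one small trial. The split probabilities assume 24 of 72 at or below 125 mmHg; the size of the shift rests on illustrative rates. The statistical analysis plan to which Section 10.3.5 defers interim details is not in the supplied text. If it or the IRT specification already covers this, the remedy is to say so in Sections 7.2 and 10.3.2.

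**What to change.** **Section 7.2.** Add: *Randomisation will be stratified centrally by the last qualifying SBP before randomisation (≤125 v >125 mmHg), in permuted blocks.* If enrolment has begun, apply this to the remaining participants. Naming the reading matters, because Section 6.1 uses at least two consecutive values over 12 hours, Section 6.2 uses SBP at randomisation, and Table 2-2 has a Day 1 pre-dose value.

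**Section 10.3.2.** Add: *Mantel-Haenszel risk difference and relative risk, stratified by the same SBP factor, with 95% confidence intervals, will be reported beside the crude estimates.* This is worth doing even if the allocation cannot be changed.

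**Cost.** An IRT configuration change, including SBP entry if it is not already captured; a few incomplete blocks; and slightly more analysis work. N stays at 72, with no added visits. The two-level factor does not balance 100 to <115 mmHg against 115 to 125 mmHg within the low band.
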